### 2.8.2 Adverse events (AEs)

Verbatim terms will be coded to lower-level terms in the Medical Dictionary for Regulatory Activities (MedDRA). AEs will be coded to MedDRA. An assessment of severity grade will be made using NCI-CTCAE v4.03. Summary tables for adverse events (AEs) will include only AEs that started or worsened during the on-treatment period, the *treatment-emergent* AEs. The incidence of treatment-emergent adverse events (new or worsening from baseline) will be summarized by System Organ Class (SOC) and or Preferred Term (PT), severity (CTC Grade 1-4, 5 Death is excluded), type of adverse event, relation to study treatment.

Since safety data collection was changed in the protocol amendment released on 18-Mar-2016, CTC grade were captured in the RDC clinical database only after the protocol amendment. All SAEs including AESIs reported as SAEs were captured in ARGUS safety database throughout the study.

Thorough manual review was implemented to ensure SAEs reported both in ARGUS and RDC databases were uniquely matched without any missing or overlapped inputs.

Hence, AEs/SAEs from both ARGUS safety database and RDC clinical database will be summarized separately to ensure comprehensive and transparent safety data reporting. Global protocol amendment date (18-Mar-2016) as a general cutoff date will be applied to analyze safety data from RDC clinical database.

The following AE summary tables will be provided:

I. from Safety Database (ARGUS):

- All SAEs throughout the study
  - SAEs regardless of study treatment relationship by primary system organ class and preferred term
  - SAEs suspected to be study treatment relationship by primary system organ class and preferred term

- All AESI reported as SAEs as per protocol throughout the study
  - Serious AESIs regardless of study treatment relationship by safety topic and preferred term

II. from Clinical Database (RDC):

- AEs (non-serious AE and AESI) after protocol amendment
  - AEs regardless of study treatment relationship
    - a. by primary system organ class, preferred term and maximum CTC grade
    - b. by primary system organ class and preferred term
  - AEs suspected to be study treatment related
    - a. by primary system organ class, preferred term and maximum CTC grade
    - b. by primary system organ class and preferred term
  - AEs leading to study drug discontinuation regardless of study drug relationship by primary system organ class and preferred term

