  - AEs resulting in dose adjustment or interruption regardless of study drug relationship by primary system organ class and preferred term
  - AEs requiring additional therapy and concomitant medication regardless of study drug relationship by primary system organ class and preferred term
  - AESIs regardless of study treatment relationship
    - c. by primary system organ class, preferred term and maximum CTC grade
    - d. by primary system organ class and preferred term
  - AESIs suspected to be study treatment related
    - c. by primary system organ class, preferred term and maximum CTC grade
    - d. by primary system organ class and preferred term
  - AESIs leading to study drug discontinuation regardless of study drug relationship by primary system organ class and preferred term
  - AESIs resulting in dose adjustment or interruption regardless of study drug relationship by primary system organ class and preferred term
  - AESIs requiring additional therapy and concomitant medication regardless of study drug relationship by primary system organ class and preferred term
- SAEs after protocol amendment
  - SAEs regardless of study treatment relationship by primary system organ class and preferred term
  - SAEs suspected to be study treatment relationship by primary system organ class and preferred term

For legal requirements of ClinicalTrials.gov and EudraCT, two required tables on treatment-emergent non-serious AEs with an incidence greater than 5% in clinical database, and on-treatment deaths and treatment-emergent SAEs in ARGUS safety database will be provided by

system organ class and preferred term using the safety set. The rule for the calculation of the number of occurrences is detailed in the Appendix section 5.2.

All of these tables will display the number and percent of patients that experience the given event and will display events by MedDRA. Events will be displayed alphabetically for SOC and PT. All safety data (including those from the post-treatment periods) will be listed and those collected during the post-treatment period are to be flagged. The following listings will also be generated:

- Listing of AEs leading to study drug discontinuation
- Listing of AEs leading to dose adjustment or interruption
- Listing of SAEs in ARGUS safety database
- Listing of SAEs in RDC clinical database

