### **2.8.2.1 Adverse events of special interest / grouping of AEs**

Adverse events of special interest (AESI) will be summarized by risk group and preferred term defined below. AESIs in RDC clinical database and serious AESI in ARGUS safety database will also be listed.

Adverse events of special interest (AESI) are defined as events (serious or non-serious) which are ones of scientific and medical concern specific to the sponsor's product or program, for which ongoing monitoring and rapid communication by the investigator to the sponsor may be appropriate. Such events may require further investigation in order to characterize and understand them.

Adverse events of special interest are defined on the basis of an ongoing review of the safety data. AESIs are discussed in detail in the Investigator Brochure.

In addition to all serious adverse events reported on a continuous basis throughout the study, the investigator should use the SAE form to report the following medically significant potential risks noted in the Novartis Risk Management Plan for everolimus:

- Development toxicity
- Reproductive (teratogenicity) toxicity
- Intestinal obstruction /ileus
- Male infertility
- Pancreatitis
- Cholelithiasis
- Muscle-wasting/Muscle-loss

All AESIs are defined through the use of MedDRA terms, Standardized MedDRA Queries (SMQ), Preferred Terms (PT), System Organ Classes (SOC), or through a combination of these components. At the project level, a SAS dataset named Case Retrieval Strategy (eCRS) contains the exact composition of the adverse events groupings will be used to map reported adverse events to the adverse events groupings of special interest. This dataset may be updated (i.e., it is a living document) based on review of accumulating trial data, and it is the most up to date version at the time of DBL that will be used. Safety topics flagged in the

eCRS are adjusted to use RMP update flag (RM) instead of core safety flag (SP), with 2 study-specific groupings of “Cholelithiasis” and “Intestinal obstruction ileus” using other flag (OS) to generate protocol-defined AESIs from both RDC clinical and ARGUS safety databases. Note that certain adverse events may be reported within multiple groupings.

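### SAP 2.8.2 says adverse events are summarized by CTC grade, but its table list leaves post-amendment SAEs without a clear place in any grade table

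*SAP*

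**What the plan says.** Table 1-1 of the SAP and Table 3-1 of the protocol define the primary endpoint by both frequency and severity, and name SAEs alongside AEs. The opening text of SAP 2.8.2 says the incidence of treatment-emergent AEs will be broken down by system organ class or preferred term, then by "severity (CTC Grade 1-4, 5 Death is excluded), type of adverse event, relation to study treatment". Protocol 10.5.3.2 has a matching sentence. Neither text excludes serious events; the SAP excludes only Grade 5.

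On data sources, SAP 2.8.2 says that "CTC grade were captured in the RDC clinical database only after the protocol amendment", and SAP 5.2 says grading does not apply to ARGUS.

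Part II of the table list, for RDC, has two blocks. The first is headed "AEs (non-serious AE and AESI) after protocol amendment" and contains all the maximum-grade tables. The second covers SAEs after the amendment and has two tables: "SAEs regardless of study treatment relationship by primary system organ class and preferred term", and the same layout for suspected-related SAEs. Neither is broken down by grade.

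A registry table covers "treatment-emergent non-serious AEs with an incidence greater than 5% in clinical database". SAP 2.8.2 also promises that "All safety data (including those from the post-treatment periods) will be listed". SAP 2.8.2.1 defines AESIs to include both serious and non-serious events. SAP section 4 declares no change from the protocol analysis.

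**The concern.** The opening text and the table list of one section describe different populations for the severity analysis. Taken at its word, the opening text puts a post-amendment Grade 3 or 4 SAE in the maximum-grade table. Taken at its word, the block heading leaves it out unless it is an AESI.

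Grades exist only in RDC and only after the amendment, so no other table can make up the difference. This list therefore decides whether SAE severity, which the primary endpoint names, is summarized at all. SAEs are also where high grades are likely to be found, so their absence bears most on the Grade 3-4 column. Two programmers working carefully from the same SAP could report different Grade 3-4 percentages from the same data.

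**Working it through.** The plan gives no figure to reproduce. The check sets the planned summaries side by side and then sizes the possible shift.

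**Step 1: are the grades available?** Protocol 8.1.1 asks for a CTCAE grade of 1 to 4, seriousness and action taken for each AE. SAP 2.8.2 confirms that RDC held grades after the amendment. The data therefore do not force the gap.

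**Step 2: where could the grade of a post-amendment, non-AESI SAE be summarized?**

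| Planned summary | Tables | With grade | Non-AESI SAE in stated scope? |
|---|---|---|---|
| ARGUS SAEs (2.8.2 part I) | 2 | 0 | yes |
| ARGUS serious AESIs (2.8.2 part I) | 1 | 0 | no |
| RDC AEs (2.8.2 part II) | 2 maximum grade + 2 SOC/PT + 3 action taken = 7 | 2 | not if the heading binds |
| RDC AESIs (2.8.2 part II) | 7, same layout | 2 | no |
| RDC SAEs (2.8.2 part II) | 2 | 0 | yes |
| Registry tables (2.8.2) | 2 | 0 | ARGUS table only |
| AESI grade summary (2.8.2.1) | not itemized | yes | no |
| Deaths (2.8.3) | 2 | 0 | fatal events only |

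If the heading binds, no row has both a grade breakdown and a scope that includes these SAEs.

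**Step 3: what can the heading mean?**

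| Reading of the parenthesis | Non-AESI SAEs in a grade table? | Serious AESIs in a grade table? |
|---|---|---|
| (a) Loose label for the newly collected AE data | yes | yes |
| (b) Non-serious AEs, plus all AESIs | no | yes |
| (c) Non-serious AEs and non-serious AESIs | no | no |

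Two of the three readings leave out non-AESI SAEs, and (c) leaves out serious AESIs too.

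**Step 4: size.** Inputs: 34 enrolled patients, of whom about 30% had AEs in RDC after the amendment (SAP 2.1); Safety Set as the analysis set (SAP 2.2). Assumption: all 34 received at least one dose.

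- Shift in the Grade 3-4 percentage for each patient whose only Grade 3-4 event is an omitted SAE: 1/34 = 0.0294, or 2.9 percentage points. In the suspected-related table the same shift applies to a patient whose only suspected-related Grade 3-4 event is such an SAE.
- Ceiling on affected patients: 0.30 × 34 = 10.2, so about 10. This takes the 30% to count serious as well as non-serious AEs in RDC.

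The documents do not give the number of patients with a post-amendment non-AESI SAE, so the actual shift cannot be computed.

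**The case against.** The best defence is reading (a). The entries under the heading say only AEs, the opening text grades AEs without restriction, and the amendment newly added non-serious AEs, so the parenthesis may just describe what was new. Where the SAP plainly wants a non-serious restriction, as in the registry table, it says so directly. On this reading nothing is lost. It is possible but not secure: the heading governs the entries below it, and SAEs have their own parallel block. What stands is that the text is unclear rather than plainly wrong.

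The weight is also limited. The study tests no hypothesis, safety is to be judged mainly on frequency, and with about 10 patients the listings would show each case.

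A reader might infer more than the documents support:

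- *All seven RDC AE tables lose information.* The two by system organ class and preferred term have direct SAE counterparts, so frequency is split across tables, not lost.
- *The SAP departs from the protocol on SAEs.* Protocol 10.5.3.2 has a separate sentence on serious events that asks only for listing and tabulation by type, which the SAP meets. The severity point rests on the general AE sentence and the endpoint.
- *The AESI tables are safe, and which SAEs are graded depends on the AESI grouping dataset, of which "it is the most up to date version at the time of DBL that will be used".* Both hold only under reading (b).
- *The Grade 3-4 percentage can only be understated.* That depends on how a fatal event without a grade is ranked. If such a row counted as worst, including SAEs could move a patient out of Grade 3-4. The SAP gives no rule.

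**Conclusion.** The concern holds as an internal inconsistency in SAP 2.8.2 on the severity part of the primary endpoint. Unless the block heading is only a loose label, post-amendment SAEs that are not AESIs reach no severity summary; if it means non-serious events throughout, serious AESIs do not either.

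The main effect is on the two AE maximum-grade tables. The possible understatement is 2.9 points of the Grade 3-4 percentage per affected patient, for at most about 10 patients. This assumes that all 34 were dosed, that the 30% figure covers serious events, and that a fatal event without a grade does not displace a recorded grade. A secondary effect is that these SAEs are missing from the three action-taken tables (discontinuation, dose adjustment or interruption, added therapy). The end-of-treatment reasons in 2.3.1 and the exposure summary in 2.8.1 cover that only in part.

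SAEs before the amendment are outside this point, because no grade was captured for them. The matter should be fixed because it touches the primary endpoint and the correction is cheap, but it does not put the data at risk.

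**What to change.** In SAP 2.8.2 part II:

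1. Retitle the first block *All AEs (serious and non-serious) after protocol amendment*, and run the AE maximum-grade and action-taken tables on all treatment-emergent RDC AEs.
2. State that the AESI tables include serious AESIs.
3. Keep the separate registry table of non-serious AEs.
4. State that a fatal SAE without a grade appears in a separate ungraded row and does not replace the patient's highest recorded Grade 1-4.

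Grade, seriousness and action taken are already collected for each AE, so no new data are needed. The cost is minor reprogramming and one added display rule.

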#### **7.1.5.1 Withdrawal of consent**

Patients may voluntarily withdraw consent to participate in the study for any reason at any time. Withdrawal of consent occurs only when a patient does not want to participate in the study any longer, and does not want any further visits or assessments, and does not want any further study related contact.

Novartis will continue to retain and use all research results that have already been collected for the study evaluation. All biological samples that have already been collected may be retained and analyzed at a later date (or as required by local regulations).

If a patient withdraws consent, the investigator should make a reasonable effort (e.g. telephone, e-mail, letter) to understand the primary reason for this decision and record this information.

Everolimus must be discontinued and no further assessments conducted.

Further attempts to contact the patient are not allowed unless safety findings require communication or follow up.

Patients may be withdrawn from the study if any of the following occur:

1. Adverse event(s).
2. Subject withdrew consent.
3. Lost to follow-up.
4. Administrative problems.
5. Death.
6. Disease progression.
7. Treatment duration completed as per protocol.
8. Protocol deviation
9. Sponsor decision

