## **8 Safety monitoring and reporting**

### **8.1 Adverse events**

#### **8.1.1 Definitions and reporting**

An adverse event is defined as the appearance of (or worsening of any pre-existing) undesirable sign(s), symptom(s), or medical condition(s) that occur after patient's signed informed consent has been obtained.

Adverse events of special interest as noted in [Section 8.1.3](#) will be reported as serious adverse events.

Abnormal laboratory values or test results occurring after informed consent constitute adverse events only if they induce clinical signs or symptoms, are considered clinically significant, require therapy (e.g., hematologic abnormality that requires transfusion or hematological stem cell support), or require changes in study medication(s).

Any ongoing adverse events from the parent study will be captured as medical history in the roll-over database. Any AE that begins (or worsens) after signing of the informed consent for the rollover and during the 30-day (or 28-day) safety follow up period defined in the parent protocol should be reported in both clinical databases.

Adverse event monitoring should be continued for at least 30 following the last dose of study treatment. Adverse events (including lab abnormalities that constitute AEs) should be described using a diagnosis whenever possible, rather than individual underlying signs and symptoms. When a clear diagnosis cannot be identified, each sign or symptom should be reported as a separate Adverse Event.

Adverse events will be assessed according to the current version of the Common Terminology Criteria for Adverse Events (CTCAE). If CTCAE grading does not exist for an adverse event, the severity of mild, moderate, severe, and life-threatening, corresponding to Grades 1 - 4, will be used. CTCAE Grade 5 (death) will not be used in this study; rather, information about deaths will be collected on the EOT page.

The occurrence of adverse events should be sought by non-directive questioning of the patient (subject) during the screening process after signing informed consent and at each visit during the study. Adverse events also may be detected when they are volunteered by the patient (subject) during the screening process or between visits, or through physical examination, laboratory test, or other assessments. As far as possible, each adverse event should be evaluated to determine:

1. The severity grade (CTCAE Grade 1-4)
2. Its duration (Start and end dates)

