3. Its relationship to the study treatment (reasonable possibility that AE is related: No, Yes)
4. Action taken with respect to study or investigational treatment (none, dose adjusted, temporarily interrupted, permanently discontinued, unknown, not applicable)
5. Whether medication or therapy was given (no concomitant medication/non-drug therapy, concomitant medication/non-drug therapy)
6. Whether it is serious, where a serious adverse event (SAE) is defined as in Section 8.2.1

If the event worsens the event should be reported a second time in the CRF noting the start date when the event worsens in toxicity. For grade 3 and 4 adverse events only, if improvement to a lower grade is determined a new entry for this event should be reported in the CRF noting the start date when the event improved from having been Grade 3 or Grade 4.

All adverse events should be treated appropriately. If a concomitant medication or non-drug therapy is given, this action should be recorded on the Adverse Event CRF.

Once an adverse event is detected, it should be followed until its resolution or until it is judged to be permanent, and assessment should be made at each visit (or more frequently, if necessary) of any changes in severity, the suspected relationship to the study treatment, the interventions required to treat it, and the outcome.

Progression of malignancy (including fatal outcomes), if documented by use of appropriate method (for example, as per RECIST criteria for solid tumors or as per Cheson's guidelines for hematological malignancies), should not be reported as a serious adverse event.

Adverse events separate from the progression of malignancy (example, deep vein thrombosis at the time of progression or hemoptysis concurrent with finding of disease progression) will be reported as per usual guidelines used for such events with proper attribution regarding relatedness to the drug.

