## **8.2 Serious adverse events**

### **8.2.1 Definitions**

Serious adverse event (SAE) is defined as one of the following:

- Is fatal or life-threatening
- Results in persistent or significant disability/incapacity
- Constitutes a congenital anomaly/birth defect
- Is medically significant, i.e., defined as an event that jeopardizes the patient or may require medical or surgical intervention to prevent one of the outcomes listed above
- Requires inpatient hospitalization or prolongation of existing hospitalization,
- Note that hospitalizations for the following reasons should not be reported as serious adverse events:
  - Routine treatment or monitoring of the studied indication, not associated with any deterioration in condition
  - Elective or pre-planned treatment for a pre-existing condition that is unrelated to the indication under study and has not worsened since signing the informed consent
  - Social reasons and respite care in the absence of any deterioration in the patient's general condition

- Note that treatment on an emergency outpatient basis that does not result in hospital admission and involves an event not fulfilling any of the definitions of a SAE given above is not a serious adverse event

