#### **10.5.3.2 Adverse events (AEs)**

Summary tables for adverse events (AEs) will include only AEs that started or worsened during the on-treatment period, the *treatment-emergent* AEs. However, all safety data (including those from the post-treatment periods) will be listed and those collected during the post-treatment period are to be flagged.

The incidence of treatment-emergent adverse events (new or worsening from baseline) will be summarized by system organ class and or preferred term, severity (based on CTCAE grades), type of adverse event, relation to study treatment.

Deaths reportable as SAEs and non-fatal serious adverse events will be listed by patient and tabulated by type of adverse event.

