## **2.3 Patient disposition, demographics and other baseline characteristics**

### **2.3.1 Patient disposition**

The number of patients ongoing, completed and discontinued from the treatment at the time of analysis as well as the primary reason for end of treatment will be summarized.

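### Registry on-treatment deaths are taken from an SAE database, while the protocol keeps documented progression deaths out of SAE reporting

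*SAP*

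**What the plan says.** SAP 2.8.2 plans two tables for the registries. One, from the clinical database, covers non-serious AEs. For the other, "on-treatment deaths and treatment-emergent SAEs in ARGUS safety database will be provided by" system organ class and preferred term. SAP 2.8.3 says that all deaths will be summarized. It then plans an on-treatment death table from RDC, a table of all deaths from ARGUS, and a listing of all deaths from ARGUS. No other dedicated death listing is planned.

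Protocol 8.1.1 sets the reporting rule: "Progression of malignancy (including fatal outcomes), if documented by use of appropriate method", "should not be reported as a serious adverse event". The same section drops CTCAE grade 5 and says that "information about deaths will be collected on the EOT page". SAP 2.8.3 and 5.2 repeat this, and SAP 5.2 names the CRF panel.

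Protocol 10.5.3.2 adds: "Deaths reportable as SAEs and non-fatal serious adverse events will be listed by patient and tabulated by type of adverse event". SAP 2.8.3 carries the part on deaths over almost unchanged.

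**The concern.** The registry death count and the table headed as all deaths come from a database that the SAP describes only as holding SAEs. The protocol tells sites not to report one class of death as an SAE, namely death from documented progression of malignancy. Under those two instructions, whether an on-treatment death reaches the public count can depend on its cause.

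This class of death is foreseeable. Treatment continues until benefit is lost, which Protocol 4.1 glosses as disease progression, and malignancies are among the indications listed in Protocol 1.2.1.2. Death soon after progression is an ordinary way to leave such a study.

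Safety is the primary objective. The RDC-based and ARGUS-based death counts can disagree, and the SAP gives no rule for reconciling deaths that are not SAEs.

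**Working it through.** The plan states no figure to reproduce, and no number of deaths appears in either document. The check is a comparison of text, followed by the weight of one patient.

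**Following one patient through the plan.** Take a patient whose malignancy progresses, documented by an appropriate method, who stops everolimus and dies of it on day 20 after the last dose.

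1. *Is the death on-treatment?* Yes. SAP 2.8 runs the on-treatment period from the first roll-over dose to 30 days after the last dose.
2. *Is it reported as an SAE?* No, under Protocol 8.1.1. The general SAE definition in Protocol 8.2.1 includes "Is fatal or life-threatening", but the rule in 8.1.1 is specific and names fatal outcomes. A death without documented progression stays an SAE.
3. *Does it reach ARGUS?* No route is stated. SAP 2.1 says that under the original protocol SAEs were collected only in ARGUS. SAP 2.8.2 says that ARGUS captured all SAEs, including AESIs reported as SAEs, throughout the study. No other feed of deaths into ARGUS is described.
4. *Where is it recorded?* On the end-of-treatment CRF page, in the clinical database.
5. *Does reconciliation bring it into ARGUS?* No. The manual matching of ARGUS and RDC in SAP 2.8.2 is described for SAEs only.
6. *Does it enter the registry table?* Not by any stated route, since ARGUS is the source named there.
7. *Does it enter the ARGUS table and listing of all deaths?* Not by any stated route, for the same reason.
8. *Does it appear elsewhere?* It can appear in the RDC on-treatment death table in SAP 2.8.3. It may not be counted as a death in disposition. SAP 2.3.1 says "the primary reason for end of treatment will be summarized", and the withdrawal reasons in Protocol 7.1.5.1 list death and "6. Disease progression" separately. If this patient's primary reason is progression, the death does not show in that summary.

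The wording in Protocol 10.5.3.2 and SAP 2.8.3 about deaths reportable as SAEs confirms that the plan itself allows for deaths that are not.

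**The RDC cutoff.** SAP 2.8.2 applies 18-Mar-2016 as a general cutoff for RDC safety data. It stands in the AE section, and the RDC death bullet in 2.8.3 carries no such limit. If it were applied to deaths, any among the 11 patients who had already discontinued by then (SAP 2.1) could drop out of the RDC table too. One clarifying sentence is enough.

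**Weight of one missed death.** SAP 2.1 gives 34 enrolled patients. The safety set requires at least one dose, and its size is not stated.

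| Assumption | Formula | Effect on displayed percentage |
|---|---|---|
| All 34 dosed, one death missed | 1/34 = 0.0294 | 2.9 points |
| Two never dosed (illustration only), one death missed | 1/32 = 0.0313 | 3.1 points |
| All 34 dosed, five deaths missed (illustration only) | 5/34 = 0.147 | 14.7 points |

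**The case against.** The strongest case on the other side has five parts.

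- **The sentence is ambiguous.** The ARGUS phrase in SAP 2.8.2 could attach to the SAEs alone, and the only table that SAP 2.8.3 titles as on-treatment death comes from RDC. This reading is possible but less natural, because the sentence pairs one table from each database. It would also leave the registry deaths with no named source, which needs the same correction.
- **The deaths are visible elsewhere.** The RDC table exists, and SAP 2.1 and 2.8.2 commit to listing all data in the database and all safety data. This stands for the study report: progression deaths are not hidden there. None of these outputs feeds the registry table.
- **The ARGUS table names its source, so its title is only a label.** This is largely fair for that table taken alone, and relabelling deals with it. It does not help the registry count.
- **The contents of ARGUS are not shown, and the triggering case is narrow.** Both points stand. The documents do not say that ARGUS holds nothing but SAEs. The exclusion needs documented progression, the visit schedule contains no tumour assessment, and death must fall within 30 days of the last dose. The claim is therefore limited to the absence of a stated route. A prespecified count should not depend on sites departing from Protocol 8.1.1.
- **The Study Evaluation Completion page is not described as recording death details, and it was added only by the amendment.** This also stands. That page can be used only where available, as a supplement to the end-of-treatment page.

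**Conclusion.** The concern holds: the plan is wrong as written. If sites follow Protocol 8.1.1 and the programmers follow SAP 2.8.2, a death from documented progression inside the on-treatment window has no stated route into the registry table or the ARGUS all-deaths outputs.

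The numerical effect is unknown and may be zero. Each missed death is worth 2.9 percentage points, on the assumption that all 34 enrolled patients are in the safety set. The conclusion rests on the stated contents of ARGUS being its actual contents as far as deaths are concerned, and on reading ARGUS as the source of the registry deaths. No hypothesis test or design decision depends on it. It should be fixed because it affects the public count of deaths in a study whose primary objective is safety, and because the remedy is small.

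**What to change.** Amend SAP 2.8.2 and 2.8.3 as follows.

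1. Define on-treatment death as death from any cause between the first roll-over dose and 30 days after the last dose.
2. Derive it with one record per patient from the RDC death information (the end-of-treatment page, and the Study Evaluation Completion page where available) combined with ARGUS. Reconcile any disagreement between the sources before database lock.
3. Use that single count both in SAP 2.8.3 and in the registry table.
4. Label the ARGUS-only table and listing as deaths reported as SAEs.
5. State that the 18-Mar-2016 RDC cutoff, written for AE data, does not apply to deaths.

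The cost is a few sentences of SAP text and a reconciliation of 34 patients, with possibly a few site queries. The RDC source panel for deaths is already named in SAP 5.2. Study conduct and SAE reporting rules do not change.
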